## 5.4 Sample Size and Power

*Cross-reference: UNC IRBIS Application Section A.8.3.*

Sample size estimates were generated to provide robust power to detect minimal clinically important differences (MCID) in reduction of opioid use between the 2 study arms.

Based on anecdotal information from the clinics participating in the study and data available from the Liebschutz and Sullivan et al. studies, a reasonable estimate of mean baseline opioid use across the planned study is 55 mg/day. Based on doses of this magnitude, providers involved with the study indicated that differences in dose reduction of 10 MED or greater were likely to be viewed as clinically meaningful. Consequently, sample size estimates were generated based on an effect size of a difference of 10 MED between the 2 intervention arms. The data available from the Liebschutz and Sullivan et al. studies indicate that a reasonable estimate of the coefficient of variation (ratio of standard deviation to the mean) for opioid dose levels is 1.45 (range of 1.19 to 1.54), suggesting that a reasonable estimate for the standard deviation of the dose level for this study is 80 MED. Finally, data from Liebschutz and Sullivan et al. suggest that correlation between the baseline and follow-up opioid use levels will result in a standard deviation of the change in opioid use of the same magnitude of the baseline standard deviation, and that controlling for baseline opioid use in an Analysis of Covariance model will reduce the residual mean square error for the test of treatment differences in the change in opioid use to no more

than 50% of the baseline level, or 40 mg/day. Based on these assumptions and an assumed minimally important difference of 10 mg/day, the number of evaluable independent participants required to achieve 80% power to detect a difference of this size is approximately 253 per study arm (total of 506), assuming no attrition.

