The data available from Liebschutz and Sullivan et al. indicate opioid doses are approximately normally distributed on the natural log (ln) scale. If the change from baseline in opioid dose is also lognormally distributed, then based on the assumptions above the standard deviation of the change from baseline ln-dose, after adjusting for baseline dose would be approximately 0.650. Correspondingly, 253 participants per study arm provides 80% power to identify a 15% relative dose reduction.

To account for potential variance inflation associated with CBT group delivery (based on a group size of 8 and an interclass correlation coefficient of 0.01) and a potential loss of follow-up information on as many as 10% to 12% of participants because of attrition, the sample size was inflated by 20% to yield a total randomized size of 304 per study arm needed for the primary outcome at 12 months. Therefore, the total study sample size will be 608 randomized participants (**Table 7**).

Additional estimates of sample size requirements were generated based on the known psychometric properties of the secondary outcomes, PROMIS physical functioning and pain interference, under the assumption that at least 80% power is desired for the PROMIS Pain Interference scales. The scoring algorithm for the PROMIS scales is designed to construct a 100-point scale with a mean of 50 and standard deviation of 10. Furthermore, studies of the properties of the instruments indicate that the minimally important difference (MID) for the physical function scale is 2 units, whereas the MID for the pain interference scale is 3.5 units. Under an assumption of independent observations, a sample size of 786 evaluable participants would be required to achieve 80% power to detect the MID of 2.0 units for the physical function scale, and a sample size of 260 evaluable participants would be required to achieve 80% power to detect the MID of 3.5 units for the pain interference scale. With the planned total of 608 randomized participants, the power for the PROMIS Pain Interference score is 96%, while the power for the PROMIS Physical Functioning scale is 57%, with a 25% increase to account for attrition or missing PROMIS scale responses. No power calculations have been specified for subgroup assessments (**Table 8**).

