6. SAMPLE SIZE DETERMINATION

Sample size estimates were generated to provide robust power to detect minimal clinically important differences (MCID) in reduction of opioid use between the 2 study arms.

A total sample size of 506 participants (253 per study arm) will provide 80% power to detect an effect size of a difference of 10 MED between the SDM and MI+CBT intervention arm using an analysis of covariance model with $\alpha=0.05$ and assuming a baseline model-adjusted standard deviation for change from baseline of 40 MED. The sample size was inflated by 20% (608 total participants; 304 per study arm) to account for potential variance inflation associated with CBT group delivery (based on a group

size of 8 and an interclass correlation coefficient of 0.01) and a potential loss of follow-up opioid prescription data on as many as 12% of participants.

For the PROMIS secondary outcome measures, the minimally important difference (MID) for the physical function scale is 2 units, whereas the MID for the pain interference scale is 3.5 units. For both instruments, we assume the standard deviation for change from baseline is 10 (see section 9.2 for a more thorough description of these secondary measures). With the planned total of 608 randomized participants and assuming 20% of those have missing PROMIS scale responses, the power for the PROMIS Pain Interference score is 96%, while the power for the PROMIS Physical Functioning scale is 57% (Table 6.1).

Note that the enrollment was slower than planned, and due to timeline constraints was stopped prior to reaching 608 randomized participants. Final study enrollment was 526 randomized participants. As of June 2023 (DSMB report), study discontinuation was at 20%;, but survey completion rate was tracking around 60% (40% missing, higher than the planned levels). Approximate post-hoc power based on the final sample size is provided in Table 6.1.

Table 6.1. Power for Primary and Key Secondary Outcomes

Total sample size	Primary aim: Power for opioid MED ¹	Secondary aim: power for PROMIS Pain Interference ²	Secondary aim: Power for PROMIS Physical Functioning ²
Planned 608	80%	96%	57%
Approximate post hoc power based on randomized (n=526)	75% based on protocol- assumed level of missing opioid prescription data	85% Based on number of completed surveys	40% Based on number of completed surveys

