7.6 Multiple Comparisons and Multiplicity

The comparison of the intervention arms for the primary outcome at 12-months is the primary formal hypothesis test (0.05 level of significance, two-tailed). Statistical significance of the 2 key secondary outcomes (PROMIS physical functioning and PROMIS pain interference at 12 months) will be assessed with adjustment for multiple comparisons using the Hochberg modification to the Bonferroni adjustment (discussed further in section 9.5.1). Primary and secondary hypothesis tests resulting in nonsignificant p-values will be interpreted as inconclusive. All other statistical comparisons between intervention arm will be considered descriptive in nature with no adjustment for multiple comparisons, and all confidence intervals will be generated using 95% bounds.

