9.3 Analysis of the Primary Outcome

The intervention effect on opioid use over time will be assessed using a linear mixed model for repeated measures (MMRM) using categorical time effects (ref: S Davis). The model will be used to generate point and interval estimates and to test differences in mean changes in opioid dose between the 2 intervention groups at 12 months (primary timepoint) and 6 and 18 months (secondary timepoints). While the primary and secondary time assessments are at 6, 12 and 18 months, all available opioid prescription data from baseline (3-month average before randomization) through 18 months will be included in the model. The model will include fixed effects for the intervention group, time interval (as a categorical variable for **3, 6, 9, 12, 15 and 18**), intervention-by-time interaction, baseline opioid dose, and the stratification effect of institution (see model statement below). For each of the post-baseline timepoints, the daily MED is the average of the time from the end of the prior interval (i.e., 12 months is the 3-month average between 9 and 12 months). (Note: an inconsistency in the protocol inaccurately lists these intervals in protocol section 5.3.1, but they are accurately listed in Protocol Section 5.2.1).

This approach will provide consistent estimates and valid inferences under missing at random (MAR) data assumptions while accounting for correlation among multiple measures on the same participant. This mixed model will improve the power of the study and the precision of all estimates by allowing all available measures for an individual to be incorporated in the analysis, even if other timepoints are missing. An intervention-arm-specific Toeplitz correlation structure will be assumed for the within-participant measures, to reflect the changing correlation of these measures over time and permit the correlation structure to differ between study arms. Note: if this model does not converge, then a Toeplitz (not intervention-specific) structure will be fit. This model is further described below:

$$Y_{ij} = \alpha + \beta_1 Time_{ij} + \beta_2 Site_{ij} + \beta_3 Intervention_{ij} + \beta_4 BaselineOpioidDose_{ij} + \beta_5 (Intervention \times Time)_{ij} + \epsilon_{ij}$$

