Where Y_{ij} is the j th measure of opioid dose in subject i , α is the intercept, β_1 through β_5 are coefficients, and ϵ_{ij} is the residual error term, and the variance-covariance matrix of the residual error terms for an individual is structured with the Toeplitz pattern such that all timepoints have the same variance estimate and all timepoints the same distance apart have the same correlation (i.e., the correlation between months 6 and 9 is assumed to be the same as the correlation between 9 and 12). Note that the protocol specified a random subject effect, but adding a random subject effect does not modify the model or model results in any way and so is excluded.

Statistical analysis modeling will be carried out utilizing SAS/STAT PROC MIXED (Littell, Milliken, Stroup, Wolfinger, & Schabenberger, 2006) with the general structure of the SAS code for this model shown below. Adjusted estimates of the change in opioid dose at each timepoint between the two interventions and corresponding 95% confidence intervals will be produced. The study's primary hypothesis will be tested by estimating the difference in the change in MED between the two intervention arms at 12 months. The study's secondary hypothesis will also be tested and associated effects estimated with the difference in LS means which estimates the average difference in the response outcome between the two intervention arms at each timepoint.

```
proc mixed data = INSPIRE_Primary method=REML;
class Unique_ID Intervention timepointN clinic
model change_OpioidDose_MED = Intervention timepointN clinic baseopioid
intervention*timepointN /s residual DDFM=KR;
repeated timepointN / type=toep group=intervention subject=Unique_ID
R RCORR;
```

```
LSMestimate 'MI-CBT vs SDM at 12 Mon'
  intervention*timepointN 0 0 0  1 0 0
                           0 0 0 -1 0 0 / CL;
  lsmeans intervention*timepointN/ diff pdiff CL;
run;
NOTE: Variable names may differ in the actual data.
```

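### The sample size allows for correlation within CBT groups, but the primary and PROMIS models do not, so the SE of the arm contrast is slightly understated (about 1.7% at the plan's ICC)

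*Protocol*

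**What the plan says.** **Design.** Protocol 6.3.1 gives Arm 2 one individual MI session and up to eight group CBT-CP sessions. Arm 1 receives SDM in individual provider visits (Protocol 6.2). Only Arm 2 is therefore grouped, which makes the design partially nested.

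**Sample size.** Protocol 5.4 starts from independence: "the number of evaluable independent participants required to achieve 80% power to detect a difference of this size is approximately 253 per study arm". It then adds 20% for attrition and for CBT-group correlation, the latter "based on a group size of 8 and an interclass correlation coefficient of 0.01". The footnote to Protocol Table 7 names within-cohort correlation as one reason for the increase. SAP 6 likewise inflates N to "account for potential variance inflation associated with CBT group delivery".

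**Analysis.** In SAP 9.3, "The model will include fixed effects for the intervention group, time interval", the arm-by-time interaction, baseline dose and institution. The only correlation is within a participant: "the variance-covariance matrix of the residual error terms for an individual is structured with the Toeplitz pattern". The code has `subject=Unique_ID` and `group=intervention`. Protocol 5.3.1 lists random effects for participant only, and the SAP drops even these as redundant. SAP 9.5.1 analyses the two PROMIS outcomes with analogous models. The supportive and sensitivity analyses in SAP 9.4 do not deal with therapy groups, and SAP 9.2 defines no CBT-group variable.

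**The concern.** The plan assumes a positive correlation when it sets N and a correlation of zero when it analyses the data. For any positive ICC, leaving out the covariance between members of one CBT group makes the variance of the Arm 2 mean too small. The CI for the arm difference is then too narrow, and the test rejects too often under the null. This bears on the single primary test ("0.05 level of significance, two-tailed") and on the two Hochberg-adjusted PROMIS tests.

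Nothing else in the model makes up for it. The institution term removes differences between sites, not between therapy groups within a site. The SAP's reason for dropping the participant effect concerns repeated measures on one person, not different people in one group.

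A p-value close to its threshold would be open to challenge from the plan's own assumption, and a group term added after the results are known would be post hoc.

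**Working it through.** **Inputs**

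- Two-sided alpha 0.05 (SAP 7.6) and 80% power (Protocol 5.4).
- Difference: "effect size of a difference of 10 MED between the 2 intervention arms".
- SD 40: "assuming a baseline model-adjusted standard deviation for change from baseline of 40 MED".
- Group size m = 8 and ICC = 0.01 (Protocol 5.4, SAP 6).
- Allocation 1:1; 304 per arm planned; up to 12% loss; 526 randomized in the end (SAP 6).
- ICCs of 0.02 and 0.05 are my assumptions, used only to show a range.

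**Step 1: reproduce the plan's N.** The normal approximation is n = 2 × (1.96 + 0.84)² × 40² / 10², about 252 per arm. The t-test version gives 253 (power 80.1%). Then 253 × 1.20 = 303.6, so 304 per arm and 608 in total. The plan's figures reproduce.

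**Step 2: check the 20%.** The design effect is DE = 1 + (8 − 1) × 0.01 = 1.07.

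- DE in both arms, plus 12%: 253 × 1.07 × 1.12 = 303.2.
- DE in both arms, divided by the retained fraction: 253 × 1.07 / 0.88 = 307.6.
- DE in Arm 2 only (average 1.035): 253 × 1.035 / 0.88 = 297.6.

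All are within 3% of 304, so the stated N covers the clustering.

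**Step 3: SE of the contrast.** With n evaluable per arm, the planned model implies Var = 40² × (2/n). With clustering in Arm 2 only, Var = 40² × (1 + DE)/n. The SE ratio is √((1 + DE)/2), whatever n and the SD are. At ICC 0.01 it is √1.035 = 1.017, so the model's SE is 1.7% too small.

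| Evaluable per arm | SE, planned model | SE, clustered | Half-width, planned | Half-width, clustered |
|---|---|---|---|---|
| 304 × 0.88 = 267.5 | 3.46 | 3.52 | 6.78 MED | 6.90 MED |
| 263 × 0.88 = 231.4 | 3.72 | 3.78 | 7.29 MED | 7.41 MED |

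**Step 4: type I error** = 2 × (1 − Φ(1.96 / ratio)).

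| m | ICC | DE | SE ratio | Type I error |
|---|---|---|---|---|
| 8 | 0.01 (plan) | 1.07 | 1.017 | 5.4% |
| 8 | 0.02 (assumed) | 1.14 | 1.034 | 5.8% |
| 8 | 0.05 (assumed) | 1.35 | 1.084 | 7.1% |
| 4.8 | 0.01 (plan) | 1.038 | 1.009 | 5.2% |

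The last row is for PROMIS: at 60% survey completion (SAP 6), a group of 8 yields 8 × 0.60 = 4.8 responders. A simulation with arm-specific variances, 33 groups of 8 and no group term gave 5.5% at ICC 0.01 and 7.2% at 0.05, in line with the formula.

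**Step 5: power.** At 304 per arm with 12% loss, power is 81.1% with clustering and 82.4% without. At 263 per arm it is 75.3% and 76.7%. Both of the latter sit close to the 75% in SAP Table 6.1, so that figure does not show whether clustering was counted.

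These are single-timepoint calculations at 12 months. They do not model the repeated measures.

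**The case against.** **The effect is tiny on the plan's own figures.** This stands. At the only documented ICC, the half-width changes by 0.12 MED against a 10 MED target, and the type I error by 0.4 percentage points.

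**Even that is near an upper bound at ICC 0.01.** This also stands. The calculation puts every Arm 2 participant in a fully evaluable group of 8. SAP 5.2 expects missed group sessions to be a main form of nonadherence, and SAP 8.1 expects many participants with no intervention visits. People who never attend share no group.

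**Nothing in the documents points to a larger ICC for dose.** This is fair. The outcome is prescribed dose from the EHR, Arm 2 participants keep their own opioid prescriber (Protocol 6.3.1), and institution is already in the model. Equally, the documents give no source for 0.01, and the planned model cannot estimate it.

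**The fix may change little.** Partly right. With 33 groups of 8 and a true ICC of 0.01, a one-way variance estimate is zero or negative about 41% of the time: P(F with 32 and 231 df < 0.99/1.07) = 0.41. A zero estimate returns the planned model. That limits the gain but does no harm.

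**Group identity may not be recorded.** This stands. Protocol Table 5, SAP 8.3 and SAP 9.2 describe attendance logs and session counts. None says that the group itself is captured or that groups were closed cohorts. A reader might infer that a cohort identifier is ready for use, but the documents do not show it.

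**Conclusion.** The mismatch between design and analysis is real, and its direction is certain for any positive ICC, which the plan itself assumes. Its size is small: the SE of the primary contrast is about 1.7% too small and the type I error at most about 5.4%, given ICC 0.01 and full groups of 8. For PROMIS at 60% completion it is about 5.2%.

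Three stronger readings are tempting but unsupported:

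- *That participant-level variance in Arm 2 is understated.* It is not. `group=intervention` lets that variance differ by arm. What is missing is the covariance between group members, which enters the variance of the Arm 2 mean.
- *That the test really runs at about 7%.* That needs an ICC of 0.05, which appears nowhere in the documents.
- *That the trial should have been larger for this reason.* The 608 target already includes the inflation.

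The case for acting is consistency and low cost, not a large expected bias.

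**What to change.** 1. Confirm that each Arm 2 participant's CBT group can be recovered from the attendance records. If membership was rolling, use the first group attended.
2. Add a random intercept for CBT group, in Arm 2 only, to the primary model and the two PROMIS models. Treat each SDM participant and each never-grouped Arm 2 participant as a singleton. Keep everyone in the randomized arm and keep `DDFM=KR`. State that a zero variance estimate returns the planned model.
3. Report the estimated ICC.
4. At minimum, if the planned models stay primary, prespecify the partially nested model or cluster-robust SEs as a sensitivity analysis in SAP 9.4, before results by arm are seen.

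**Cost:** one identifier to derive, one extra model statement, and a slightly wider CI. At the plan's ICC, the primary half-width grows by about 0.12 MED. N does not need to change for this point.

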**Table 7. Sample Size Required to Obtain 80% Power for Primary and Key Secondary Outcomes**

Parameter	Mean difference between groups for change from baseline	SD	Power	N (total)	Percentage increase to account for 1-year attrition and within-cohort correlation	N with increase for attrition*
Average Daily MED	10	40	80%	506	20%	608
PROMIS Pain Interference Scale	3.5	10	80%	260	25%	350
PROMIS Physical Functioning Scale	2	10	80%	786	25%	1060

\*The n is increased by 20% in the calculation to account for expected within-cohort correlation and attrition from the study before the primary 12-month timepoint. A further 5% attrition was assumed for the PROMIS scales collected via web or phone.

**Table 8. Power for Primary and Key Secondary Outcomes with N=608 Randomized Participants**

Total sample size	Primary aim: Power for opioid MED*	Secondary aim: power for PROMIS Pain Interference*	Secondary aim: Power for PROMIS Physical Functioning*
608	80%	96%	57%

\*MID, SD, and loss to follow-up rates are the same as noted in Table 7.

## 5.5 Interim Analysis

The Data and Safety Monitoring Board (DSMB) will routinely monitor the study for safety, conduct, and fidelity assessments of GCC, SDM, and CBP-MI with details of the monitoring approach specified in the **DSMB Charter** (see Appendix), the Data and Safety Monitoring Plan (DSMP), and the Statistical Analysis Plan. The DSMB will not formally monitor efficacy or effectiveness outcomes for purposes of stopping the study early (either due to demonstrated efficacy or futility).

## 6 STUDY INTERVENTION

*Cross-reference: UNC IRBIS Application Section B.3.5.*

This section describes the 2 interventions we will compare for managing CNCP patients on COT: a guideline-concordant pharmacotherapy approach with SDM (Arm 1) compared with a guideline-concordant pharmacotherapy approach with MI and CBT for chronic pain (Arm 2). Both arms of the intervention will be integrated into the usual workflow of the clinics. The first three months of the SDM intervention are the most intensive, similar to how the first three months of the CBT arm are the most intensive.

Participants in each of the study arms will receive guideline-concordant care (GCC), based on CDC clinical guidelines for COT for CNCP at their opioid management visits for the 12-month intervention period.

In light of the COVID-19 outbreak, the study will take measures to protect research participants, researchers, and the larger community from risk of infection.

Participant research visits will be performed remotely when appropriate and possible, via phone or telehealth/telemedicine. Telehealth services used will meet the study's security level clearance. The content of the interventions in the study will remain unchanged. Each institution will work with their IT departments to ensure they are using the telehealth services according to the institution's policy.

Participants who are currently enrolled in the trial will be given information about the change, the reasons for the change, and how the changes may impact their research activities. We will notify participants of the changes via phone call, letter, email, etc. and we will document how we notified them (see attached, Information for Participants on the INSPIRE study and COVID-19).

### 6.1 Guideline Concordant Care Intervention

CDC guidelines for treating adult patients for chronic pain in outpatient settings were developed to "improve communication between clinicians and patients about the benefits and risks of using prescription opioids to treat chronic pain; provider safer, more effective care for patients with chronic pain; and help reduce opioid use disorder and overdose." As a guideline for providers, the intervention content is primarily directed toward the providers participating in the study. The guidelines give guidance about medication selection, dose and duration, when and how to assess progress, and discontinue medication if needed. They support the patient-provider team to jointly assess the benefits and risks of prescription opioid use. Participants in each study arm will receive guideline-concordant pharmacotherapy treatment, based on clinical guidelines for opioid therapy for CNCP.

GCC specifies current best practices for primary care providers who are treating COT. The best practices include the following:

- *Determining when to initiate or continue opioids for chronic pain*
  - Not using opioids as first-line therapy (not applicable in this study, as participants will already be taking opioids)
  - Establishing goals with the patient for pain and function
  - Discussing risks and benefits with the patients

- *Determining opioid selection, dosage, duration, follow-up, and discontinuation*
  - Using immediate-release opioids when starting (not applicable if participants are already taking opioids)
  - Using the lowest effective dose
  - Prescribing short durations for acute pain
  - Evaluating benefits and harms frequently
- *Assessing risk and addressing harms*
  - Using strategies to mitigate risk—including patient risk assessment for prior SUDs and offering naloxone if increased risk or concurrent benzodiazepine use are present
  - Periodically reviewing state PDMPs to determine if patient is filling prescriptions or receiving opioid dosages elsewhere
  - Using UDT at least annually: UDTs are part of the opioid prescribing guidelines, which are now the standard of care for providers who prescribe opioids. They are not part of the intervention. Some clinics may use point of care UDTs, others may choose clinical laboratory tests in which the results will not be available during the clinic visit in which the urine was obtained. This will be up to each clinic on how they choose to handle the UDTs.
  - Avoiding concurrent opioid and benzodiazepine prescribing
  - Offering treatment for opioid use disorder

